### 1.9.2 Methodology

This is a Phase 1, multicenter, open-label, dose-escalation study in hospitalized, bleeding, and thrombocytopenic patients. Patients with modified WHO Grade 1 (see note following Table 1. Cohort Assignment) or Grade 2 bleeding due to hematology/oncology diseases or bone marrow aplasia secondary to cancer chemo/radiotherapy will be enrolled on study and treated with allogeneic Thrombosomes (See

Appendix A- Modified WHO Bleeding Score). Patients with WHO Grade 0, 3, or 4 bleeding do not meet eligibility criteria for enrollment. The protocol will require three cohorts of patients consisting of 8 patients in each cohort for a total of 24 patients (See Table 1. Cohort Assignment).

Table 1. Cohort Assignment				
Cohort	1	2	3	Total
	n	n	n	n
WHO Grade 1*or 2	8	8	8	24

Note: \*Only a subset of patients with Grade 1 bleeding who have either epistaxis, hematuria, oral petechiae, oropharyngeal bleeding, or bleeding at invasive or other wound sites.

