### **1.9.2.1 All Cohorts**

Informed consent will be obtained from thrombocytopenic (platelet count  $\geq$  5,000/  $\mu$ L and  $\leq$  70,000 per  $\mu$ L) patients who are actively bleeding or are at risk of active bleeding within the 4 weeks of initial screening. Patients are eligible who have had a documented bleeding episode(s) within the previous 4 days of screening. If they pass screening, they will be enrolled and infused. Patients who are not actively bleeding, but who are at risk for active bleeding based on medical history and prognosis (projected clinical course) within 4 weeks from their initial screening, will be monitored for active bleeding. If the patient was not actively bleeding at the time of screening, but bleeding occurs within 4 days (+ 6 hours) of initial screening, the patient does not need to be rescreened, but must have a WHO bleeding assessment and a CBC at baseline. If the patient was not actively bleeding at the time of screening, but bleeding occurs greater than 4 days and within 4 weeks of initial screening, the patient will be rescreened, enrolled and infused. Patients who are not infused within 4 weeks of initial screening are withdrawn from study. Patients who were withdrawn from study may be re-entered into study if they were: 1) previously not infused with Thrombosomes, and 2) meet all the enrollment requirements of study. All enrolled patients will be assigned to cohorts based on order of enrollment and timing of infusion of Thrombosomes.

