All enrolled patients with active bleeding of modified WHO Grade 1 (subset of patients with either epistaxis, hematuria, oral petechiae, oropharyngeal bleeding, or bleeding at invasive or other wound sites) or Grade 2 bleeding will receive Thrombosomes. Grades 0, 3, or 4 bleeding are not inclusion criteria for enrollment. Active bleeding is defined as to occur within 4 days of infusion. If the patient progresses to grade 3 or 4 bleeding during that time, they will be excluded from the study and will not be infused. Doses will be adjusted per weight of each patient. The starting dose for patients in Cohort 1 will be approximately 5 ml of Thrombosomes or approximately  $9.45 \times 10^7$  particles/kg or 165 TGPU per kg by IV infusion. The dose for patients in Cohort 2 will be approximately 10 ml of Thrombosomes or approximately  $1.89 \times 10^8$  particles/kg or 330 TGPU per kg by IV infusion. The dose for patients in Cohort 3 will be one dose of approximately 20 ml of Thrombosomes or approximately  $3.78 \times 10^8$  particles/kg or 660 TGPU per kg by IV infusion. See Table 2.

Pre-infusion, infusion (Day 1), and post-infusion follow up through Day 30 (+2 days) will be performed as outlined in *Table 4* below. Patients require observation at a minimum through the completion of Visit 4 (6 hours post-infusion). Patients may be admitted and observed overnight at the discretion of the PI. If the subject is an in-patient on Days 3-5, he/she should be assessed and samples collected as described in Table 4.

All patients in each cohort will be evaluated for any signs of AEs, serious adverse events (SAEs) and serious adverse drug reactions (SADRs) after infusion.

Patient infusions cannot occur on the same day. Once an enrolled patient has been infused, he/she must reach Day 4 without a suspension or stopping rule (1.9.8 Stopping Rules and Procedures for Study) event being reported prior to a subsequent patient being infused. In addition, there will be at least a two-week interval between cohorts to allow an independent Data Monitoring Committee (DMC) to review all patients' accumulated safety data after visit Day 6 from Cohort 1 and then again after the last patient from Cohort 2 has completed visit Day 6 in order to recommend whether the study should advance to the next cohort. Refer to Appendix B- Flow Diagram of Study Events.

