**Table 1 – Patient Cohort Assignment, Target Dose, and Safety Margins**

Cohort	No. of Infusions	Target Mean Particles/kg	Target Mean TGPU/kg	Estimated Total Volume Infused 	Safety Margin 	
					Infused Particles/kg	Infused TGPU/kg
Cohort 1 (patients 1-8)	1	$9.45 \times 10^7$	165	4.1 mL	300	301
Cohort 2 (patients 9-16)	1	$1.89 \times 10^8$	330	8.2 mL	150	150
Cohort 3 (patients 17-24)	1	$3.78 \times 10^8$	660	16.4 mL	75	75

Abbreviation: TGPU, thrombin generation potency units.

 Estimated Total Volume Infused is based on a 70-kg patient and mean Thrombosomes concentration (across lots) of  $1.61 \times 10^9$  particles/mL with associated 2,800 TGPU/mL. Doses will be adjusted by patient weight in order to maintain the target Thrombosomes particle count per kg of patient body weight. Formula: Total Volume Infused in mL = ([patient weight in kg] x [desired dose in particles/kg or TGPU/kg, specific for the cohort]) ÷ Thrombosomes particles/mL or TGPU/mL provided with the specific lot of Thrombosomes. Example for Cohort 1: 4.1 mL = ([70 kg] x [ $9.45 \times 10^7$  particles/kg]) ÷  $1.61 \times 10^9$  particles/mL.

 Safety margins are based on the single acute toxicity study in New Zealand white rabbits (see CSP Section 1.7).

Written informed consent will be obtained from patients who are either actively bleeding or at risk of bleeding within 4 weeks following screening. Patients who are actively bleeding and determined through screening assessments to meet eligibility criteria for study participation will be immediately scheduled for infusion with Thrombosomes to occur within 4 days of screening. Patients who are not actively bleeding during screening but are at risk for bleeding within 4 weeks, based on medical history and projected clinical course, will be monitored for bleeding. If bleeding begins within 4 days (+6 hours), complete rescreening will not be necessary, but updated WHO bleeding assessment and complete blood count (CBC) tests will be required for determination of eligibility. If bleeding begins >4 days later but within 4 weeks of initiation of screening, rescreening (inclusive of all original screening assessments) will be necessary for

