determination of eligibility. Given determination of eligibility through either scenario (i.e., completion of updated screening or rescreening assessments), the patient will be immediately scheduled for infusion with Thrombosomes to occur within 4 days. Patients who are not infused within 4 days of eligibility determination will (re-)enter rescreening, if no more than 4 weeks have passed since initiation of screening. Patients who are not infused within 4 weeks of initiation of screening will no longer be actively monitored for study eligibility or scheduled for infusion. However, they may subsequently re-enter the screening process at any time, if actively bleeding or determined to be at risk of bleeding. Patients will be classified as enrolled in the study at the onset of infusion.

Activities and assessments relating to the pre-infusion (screening) period, infusion (Day 1), and the post-infusion period (follow-up through Day 30 +2 days) will be performed as indicated in **Table 2** (see Section 3.3, Summary of Activities and Assessments). Importantly, stipulations exist concerning patient enrollment and the performance of assessments. For instance, patient infusions cannot occur on the same day. Once an eligible patient has been infused, the patient must reach Day 4 without a suspension or stopping rule event being reported before a subsequent patient may be infused (see Section 3.2, Safety Assessments). In addition, a 2-week interval of non-enrollment (i.e., no infusions), with all patients on study having completed the planned Day-6 follow-up visit (on Day 6 +4 days), must be met between cohorts to allow for an independent Data Monitoring Committee (DMC) to review all safety data from the previous cohort and provide recommendations on whether the study should advance to the next cohort (see **Appendix 1**).

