Abbreviations: ABO, blood types A, B, and O; AE, adverse event; ALT, alanine transaminase; aPTT, activated partial thromboplastin time; AST, aspartate transaminase; BUN, blood urea nitrogen; CBC, complete blood count; EKG, electrocardiogram; GGT, gamma glutamyl transferase; hs, high sensitivity; INR, international normalized ratio; LDH, lactate dehydrogenase; MPV, mean platelet volume; PF, prothrombin fragment; PT, prothrombin time; RBC, red blood cell; Rh, Rhesus; ROTEM, rotational thromboelastometry; SAE, serious adverse event; TAT, thrombin antithrombin; TEG, thromboelastography; TGA, thrombin generation assay; WBC, white blood cell; WHO, World Health Organization.

-  Complete rescreening will be performed on patients who preliminarily met eligibility criteria but were not actively bleeding at the time of initial screening and then started bleeding within 4 weeks. Patients who continue/begin bleeding and fully meet eligibility criteria within 4 days (+6 hours) of initial screening will not need require rescreening, except for re-assessment of WHO bleeding and CBC.
-  Baseline may occur within 24 hours following initial screening (or rescreening). The WHO bleeding severity, CBC, and coagulation assessments are required at baseline, not more than 2 hours prior to infusion. Red cell transfusion must be specifically related to treatment of bleeding within 24 hours of onset of bleeding.
-  Chart review for SAEs will occur from Day 1 through Day 30 (+2 days). Phone calls with the patient will occur to confirm whether the patient experienced an SAE or required emergency medical care at an outside facility.
-  Complete physical examinations will include measuring height and weight, documenting medical history, and performing a general medical/neurological examination. Medical history will include previous transfusions with red blood cells, plasma, and/or platelets.
-  Abbreviated physical examinations will include general appearance, cardiovascular, respiratory, extremity, abdomen, and head and neck assessments.

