### 8.2 WHO Bleeding Severity Scores

Within multiple tables, the numbers and percentages of patients will be presented by highest WHO bleeding severity score (no bleeding/grade 0, grade 1, grade 2, grade 3, or grade 4), with "highest severity score" defined as the score associated with the most severe bleeding site (given documentation of multiple sites) for the nominal time-point of interest. This distribution of highest WHO bleeding severity scores not only will be presented by nominal time-point but also will be presented by post-baseline time-points relative to baseline time-point (to allow for assessment of shift) and by both bleeding site and time-point. Differences between patient cohorts (dose levels) in the proportion of the study population showing grade 2 or higher bleeding severity for the most severe bleeding site will be tested for statistical significance per time-point using Fisher's exact test, with results displayed in a single table. To facilitate visual examination of trends, 1 or more of the summaries described above may be presented within supplementary clustered bar charts or line chart overlays.

The numbers and percentages of patients will also be presented by grade-level change in WHO bleeding severity (-2, -1, 0, +1, +2, and +3) from baseline to post-baseline time-points for the patient's most severe bleeding site at baseline, by indication of increased bleeding severity from baseline to post-baseline time-points for the patient's most severe bleeding site at baseline, and by

indication of development of new bleeding sites from baseline to post-baseline time-points. Lastly, the details of all WHO bleeding assessments will be presented in a patient-level data listing. To facilitate, within this listing, visual examination of possible post-infusion changes in bleeding severity or number of bleeding sites as associated with protocol-defined windows for the timing of infusion relative to screening (i.e., within 24 hours [as stipulated in CSP v1.1] vs. within 4 days [as stipulated in CSP v2.0+]), the data listing will be sorted first by the screening assessment dates of patients and then, within individual patients, by assessment date.

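### A patient whose bleed has stopped can be infused at baseline Grade 0, and SAP 8.2 has no rule for such a patient in its two tracked-site WHO tables

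*Protocol*

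**What the plan says.** **Eligibility.** Protocol 1.9.2 says: "Patients with WHO Grade 0, 3, or 4 bleeding do not meet eligibility criteria for enrollment". Protocol 1.9.2.1 and inclusion criterion 4 (1.11.1) repeat that Grade 0 does not qualify. Protocol 1.9.2.1 also says: "Patients are eligible who have had a documented bleeding episode(s) within the previous 4 days of screening", and: "Active bleeding is defined as to occur within 4 days of infusion". For a change of grade before infusion it gives one rule: "If the patient progresses to grade 3 or 4 bleeding during that time, they will be excluded from the study". It has no matching sentence for a fall to Grade 0.

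**Timing.** Under SAP 3.1, a patient who is bleeding and eligible at screening "will be immediately scheduled for infusion with Thrombosomes to occur within 4 days of screening". SAP 3.1 also says: "Patients will be classified as enrolled in the study at the onset of infusion". On the baseline grade, SAP Table 2, footnote 2, says: "The WHO bleeding severity, CBC, and coagulation assessments are required at baseline, not more than 2 hours prior to infusion". Protocol Table 4, footnote 2, agrees. SAP 6.3 takes the last pre-infusion assessment as baseline.

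**Analysis.** SAP 8.2 counts patients "by grade-level change in WHO bleeding severity (-2, -1, 0, +1, +2, and +3) from baseline to post-baseline time-points", for the site that was worst at baseline, and separately counts those whose grade at that site rose. These are Tables 14.3.3.5 and 14.3.3.6, both on the Safety Population, which is every infused patient (SAP 5.2). If sites tie at baseline, SAP 8.2 compares their scores at each later visit in turn and selects the higher-scoring site once the tie breaks.

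**The concern.** The entry window is 4 days, but the baseline grade describes a much shorter period. In Appendix A of the protocol, the oropharyngeal, epistaxis and invasive-site items count bleeding in the previous 24 hours. A nosebleed that stopped two days before infusion meets the definition of active bleeding, yet it can score Grade 0 at baseline.

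Such a patient cannot improve. If counted in the tracked-site tables, the patient lowers the improvement share for reasons unrelated to the product. If the sites are recorded as 0, all are tied, and the tie rule chooses the site using post-infusion scores. The baseline reference is then picked by the outcome, and always towards worsening.

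SAP 2.2.1 lists these summaries among the primary endpoints, and the protocol's secondary objectives include the effect on WHO score. The cohorts have 8 patients each, so one or two such patients move a percentage visibly. SAP 8.2 notes that the screening-to-infusion window widened from 24 hours to 4 days between protocol versions, but responds only by choosing a sort order for a listing.

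**Working it through.** **1. Reproduce the SAP's change categories.** Change = post-baseline grade (0 to 4) minus baseline grade.

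- Baseline 1: 0-1 to 4-1, that is -1 to +3.
- Baseline 2: 0-2 to 4-2, that is -2 to +2.
- Together: -2, -1, 0, +1, +2, +3, exactly the SAP's list.
- Baseline 0: 0 to +4. No negative value is possible, and +4 is not on the list.

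The categories therefore fit baseline Grade 1 or 2 only.

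**2. Can baseline Grade 0 occur?** There are two routes in.

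- Patients bleeding at or shortly before screening: a past episode is enough under Protocol 1.9.2.1, and SAP 3.1 then allows up to 4 days to infusion.
- Patients who start to bleed after screening: SAP 3.1 uses an updated WHO assessment (or a rescreen) to settle eligibility, then again allows up to 4 days to infusion.

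On neither route is the grade taken within 2 hours of infusion named as the one that decides eligibility.

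**3. Effect on Table 14.3.3.5.** Let k of the 8 patients in a cohort be at Grade 0 and counted. The largest possible improvement share is (8-k)/8. If half of the patients with a bleeding site truly improve (an assumption), the table shows 0.5 × (8-k)/8.

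| k | Largest possible share | Shown if the true share is 50% |
|---|---|---|
| 0 | 100% | 50% |
| 1 | 87.5% | 43.8% |
| 2 | 75% | 37.5% |
| 3 | 62.5% | 31.3% |
| 4 | 50% | 25% |

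**4. Effect on Table 14.3.3.6.** Let w of the other 8-k patients worsen at their tracked site. The share shown runs from w/8 (no Grade 0 patient counted as worse) to (w+k)/8 (the tie rule finds a bleeding site in each). For illustration, take w = 1 and k = 2: 1/8 = 12.5% to 3/8 = 37.5%. Among patients with a baseline site it is 1/6 = 16.7%.

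**5. The tie rule at Grade 0.** Suppose sites A and B both score 0 at baseline and at 1 hour, and at 6 hours A scores 1 and B scores 0. The rule selects A, with a change of +1. Had B been followed, the change would be 0. Neither choice can give an improvement.

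**6. How likely is k of at least 1?** The documents give no share. If a fraction p of infused patients were at Grade 0, the chance of at least one in a cohort is 1-(1-p)^8: 57% for p = 10%, 83% for p = 20%, 94% for p = 30%. These values of p are assumptions.

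**The case against.** The strongest reply is that the protocol rules Grade 0 out in three places and the SAP sets enrolment at the start of infusion. Read together, a patient at Grade 0 when infusion begins is ineligible, and the -2 to +3 list is correct. That reading is fair. It means a reader who infers that the protocol knowingly admits Grade 0 patients goes too far: the text conflicts with itself. But the conflict is not resolved anywhere, and the tables include every infused patient, so a patient infused in deviation stays in them.

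Other replies also stand in part.

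- A reader might infer that cohorts with different Grade 0 shares cannot be compared. The documents do not support this. Table 14.3.3.1 gives highest grade by visit, including Grade 0, for each cohort. Table 14.3.3.3 gives shifts by baseline grade, Table 14.3.3.7 covers new sites, and a listing gives patient detail.
- A reader might take tracked-site change as the SAP's main bleeding measure. It is one of several listed together. The only WHO test in the SAP is Fisher's exact test on Grade 2 or higher, which needs no baseline site.
- Grade 0 patients are at risk of worsening, so dropping them outright could hide safety events. This is right, and the fix has to allow for it.
- With no baseline site, these patients might simply fall out as missing, and no cap would arise. SAP 6.3 has such a rule for quantitative change, but SAP 8.2 does not say which treatment applies.
- Not every earlier bleed falls to Grade 0: oral petechiae and microscopic hematuria carry no 24-hour limit.

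**Conclusion.** The point holds, within limits. The eligibility text conflicts with the 4-day definition of active bleeding, and the SAP has no rule for a Grade 0 baseline in Tables 14.3.3.5 and 14.3.3.6. If such patients are counted there, the improvement share in a cohort of 8 is capped at (8-k)/8, and the tie rule can push the result further towards worsening.

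This rests on two things the documents leave open: that at least one patient is infused at Grade 0, and that such patients are counted rather than set to missing. The values of k used here are illustrations. The other WHO summaries show Grade 0 patients openly, so the point does not extend to the bleeding analysis as a whole. It is worth settling before database lock, because the rule is simple and should not be chosen after the grades are seen.

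**What to change.** In SAP 8.2:

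- Compute tracked-site change and increased severity among patients with baseline Grade 1 or higher, and print that denominator for each cohort.
- Add a separate row per cohort for patients at baseline Grade 0, giving their number, how many developed bleeding after infusion, and the highest grade reached. No worsening is then lost.
- State that the tie rule does not apply to sites scored 0 at baseline.

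With these rules the -2 to +3 list is complete for eligible baseline grades, and a +4 category is not needed.

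In the protocol, reconcile the 4-day definition of active bleeding and the past-episode route with the statements that Grade 0 is not eligible, and say which pre-infusion assessment decides. Which rule to adopt is for the sponsor and investigators.

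No new data are needed. The cost is smaller denominators in two tables.

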## **1.11 Inclusion /Exclusion Criteria**

### ***1.11.1 Inclusion Criteria***

1. Males and non-pregnant/non-breastfeeding females at least 18 - 74 years of age.
2. Ability to comprehend the study procedures and signed informed consent.
3. Diagnosed with any the following: acute leukemia (ALL or AML), myelodysplasia, aplasia, and/or therapy (chemotherapy or radiation) induced bone marrow aplasia or hypoplasia with thrombocytopenia (see #6 below) for a minimum of 2 days. Patients who have received either autologous or allogeneic bone marrow transplant, peripheral, or cord blood stem cells may be enrolled if they do not have chronic or acute graft-versus-host disease (GVHD).
4. WHO Grade 1 (subset) or 2 bleeding or at risk for same within 4 weeks of screening. Subset of patients with Grade 1 bleeding are those who have either epistaxis, hematuria, oral petechiae, oropharyngeal bleeding, or bleeding at invasive or other wound sites. WHO Grades 0, 3 or 4 are not inclusion criteria for eligibility.
5. If not hospitalized, willing to be observed in a clinic up to the 6-hour post-infusion time point. Patients may be admitted and observed in the hospital overnight at the discretion of the PI.
6. Thrombocytopenia with platelet count  $\geq 5,000/\mu\text{L}$  and  $\leq 70,000/\mu\text{L}$ .
7. Has permanent address and phone/email for contact and notifications, and available for the duration of the trial, which is expected to be a maximum of 8 weeks.
8. Agrees to not take any nonsteroidal inflammatory drugs within 5 days prior to infusion and during the 6 Day study follow-up period.
9. Agrees to not take any aspirin or aspirin containing drugs within 5 days prior to infusion and during the 6 Day study follow-up period.

10. Agrees to not take any COX-2 inhibitor drugs within 5 days prior to infusion and during the 6 Day study follow-up period.
11. Female patients must have a negative pregnancy test prior to enrollment and during study. Women who are postmenopausal for at least 1 year (>12 months since last menses) or are surgically sterilized do not require this test.

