**Table 4. Schedule of Events**

Evaluation	Initial Screen	Rescreen (if applicable  )	Day 1  Base Line -2 hr pre-infusion	1 hr post infusion ± 15min	6 hr post -1 or +2 hr	Day 2 24 hr post ± 3 hr	If hospitalized			Day 6 (+ 4 days)	Day 30 (+2 days) (by phone)
							Day 3	Day 4	Day 5		
Visit #	1	1A	2	3	4	5	6	7	8	9	10
Sign ICF	X										
Verbal reconfirmation of informed consent		X	X	X	X	X	X	X	X	X	X
History and complete physical exam 	X										
WHO assessment	X	X	X	X	X	X				X	
Abbreviated physical exam 		X	X	X	X	X				X	
Pregnancy test (serum or urine)-applicable females only	X	X									
Concomitant medications (Medications, OTC Remedies, Herbal Preparations,	X	X	X	X	X	X	X	X	X	X	

Evaluation	Initial Screen	Rescreen (if applicable  )	Day 1  Base Line -2 hr pre-infusion	1 hr post infusion ± 15min	6 hr post -1 or +2 hr	Day 2 24 hr post ± 3 hr	If hospitalized			Day 6 (+ 4 days)	Day 30 (+2 days) (by phone)
							Day 3	Day 4	Day 5		
Vitamins, Supplements and IV fluids)											
Record transfused blood products 	X	X	X	X	X	X	X	X	X	X	
Infusion			X								
Vital signs (pulse, BP, RR, temp)	X	X	X	Prior to infusion and then every 15 min ±5 min after the start of infusion until 2 hrs; continue every hour ±5 min until 4 hrs, then at 6 hrs, and 24 hrs post infusion.						X	
Pulse-Ox			X	Continuously monitor while monitoring for vital signs; record at same time points as for vital signs above.							
Monitor for AE			X	Prior to infusion and then every 15 min ±5 min after the start of infusion until 2 hrs; continue every hour ±5 min until 4 hrs, then at 6 hrs, and 24 hrs post infusion, ±10 mins for all other time points. Daily until discharged or Day 6.			X	X	X	X	X 
12-Lead EKG	X		X 		X						

Evaluation	Initial Screen	Rescreen (if applicable  )	Day 1  Base Line -2 hr pre-infusion	1 hr post infusion ± 15min	6 hr post -1 or +2 hr	Day 2 24 hr post ± 3 hr	If hospitalized			Day 6 (+ 4 days)	Day 30 (+2 days) (by phone)
							Day 3	Day 4	Day 5		
Hematology CBC (if blood products are transfused, then CBC pre and post transfusion)	X	X	X	X	X	X	Minimum is daily CBC			X	
ABO group, Rh type	X										
Coagulation Tests: PT/INR, aPTT, D-dimer, Fibrinogen, TAT, PF 1+2, TEG or ROTEM, TGA	Only PT/INR, aPTT, D-dimer, Fibrinogen	Only PT/INR, aPTT, D-dimer, Fibrinogen	X	X	X	X					

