**Table 3 – List of Nominal Visits and Time-Points**

Nominal Visit/Time-Point	Scheduled Study Day	Day/Time Window
Screening 	Days -28 to Day -1	Any time during Days -28 to Day -1
Baseline	Day 1	Any time pre-infusion during Day 1 
Thrombosomes Infusion	Day 1	None; represents time-point 0 and provides reference for nominal visits and time-points
1-hour post-infusion	Day 1	±15 minutes
6-hour post-infusion	Day 1	-1 to +2 hours
24-hour post-infusion	Day 2	±3 hours
Day 3 	Day 3	Any time during Day 3
Day 4 	Day 4	Any time during Day 4
Day 5 	Day 5	Any time during Day 5
Day 6	Day 6	+4 days (any time during Days 6-10)
Day 30	Day 30	+2 days (any time during Days 30-32)

 If the patient is not actively bleeding at the time of screening but bleeding occurs within 4 days (+6 hours) of initial screening, the patient will not be rescreened (just WHO bleeding severity and CBC assessments will be repeated). If the patient is not actively bleeding at the time of screening but bleeding occurs >4 days and within 4 weeks of initial screening, the patient will be wholly rescreened and, following verification of eligibility, then enrolled and infused.

 Baseline assessments may occur any time preceding infusion on Day 1, except for the assessments of WHO bleeding severity, CBC, and coagulation. These assessments will be required to occur within the 2 hours preceding infusion.

 Relevant only if the patient is hospitalized.

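### For patients out of hospital after Day 2, no contact is scheduled before the Day 4 gate, so the next same-dose infusion can be released on silence

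*Protocol*

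**What the plan says.** **The gate.** Protocol 1.9.2.1 staggers infusions within a cohort: the prior patient must reach Day 4 with no suspension or stopping rule "event being reported prior to a subsequent patient being infused". SAP 3.1 has the same condition: "the patient must reach Day 4 without a suspension or stopping rule event being reported before a subsequent patient may be infused".

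**Who is observed, and for how long.** Section 1.9.2 describes a "dose-escalation study in hospitalized, bleeding, and thrombocytopenic patients". Inclusion criterion 5, however, admits outpatients: "If not hospitalized, willing to be observed in a clinic up to the 6-hour post-infusion time point". Section 1.9.2.1 makes observation compulsory only through Visit 4, at 6 hours, and leaves an overnight stay to the investigator.

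**Days 3 to 5.** Section 1.9.2.1 says: "If the subject is an in-patient on Days 3-5, he/she should be assessed and samples collected as described in Table 4". In Table 4 these columns sit under a hospitalization heading, and adverse event monitoring runs "Daily until discharged or Day 6". SAP Table 3 annotates Day 3 with "Relevant only if the patient is hospitalized". Days 4 and 5 carry the number of the baseline footnote there, apparently a slip. The next visit for everyone is Day 6, with a window to Day 10.

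**Other routes.** Section 1.15.1 gives patients an emergency number and advises them to go to an emergency room if needed. The SAE reporting clock in 1.22.6.4 is 24 hours and starts when the investigator becomes aware.

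**The concern.** Dosing one patient at a time is meant to reveal a serious product reaction before the next patient gets the same dose. A gate that turns on the absence of a report does this only if someone is placed to notice the event. For a patient who was never admitted, or who was discharged by Day 2, nobody is scheduled to look between the 24-hour visit and Day 6 to 10, and the gate opens on Day 4.

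The exposed events are a death, a thrombotic or embolic event, or acute lung injury that starts after the 24-hour visit and is not phoned in. The suspension rule in 1.9.8, for other SAEs at least possibly related to the product, has no time limit and is exposed in the same way. Such an event could come to light only at the Day 6 visit, possibly after another infusion. The protocol sees that sites may not hear of outside care: the Day 30 call (Table 4, note 3) exists partly to ask about it.

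A separate and smaller point concerns wording. SAP 3.2 requires a stopping event to be reported within 48 hours (4 hours for anaphylaxis), whereas Protocol 1.9.8 turns on when it occurs.

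**Working it through.** The plan states no figure for this point and gives no statistical basis for its sample size. The check is therefore schedule arithmetic.

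**Inputs**
- 24-hour visit ±3 h, so 21 to 27 h; Day 6 visit on Days 6 to 10 (Protocol Table 4, SAP Table 3).
- Gate at Day 4 (Protocol 1.9.2.1, SAP 3.1).
- Stopping window 48 h, or 4 h for anaphylaxis (Protocol 1.9.8).
- Study day counted by calendar date, with infusion on Day 1 (SAP 6.3).
- Three cohorts of 8.
- Assumption: infusions take place between 08:00 and 20:00.

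**1. Part of the stopping window without scheduled contact**
- Out of hospital after Day 2: 48 − 27 = 21 h (43.8%) to 48 − 21 = 27 h (56.3%). This is a share of time, not of risk.
- Discharged on Day 3: with infusion at clock hour t, Day 3 opens 48 − t hours later, which is 40 h (t = 8) to 28 h (t = 20). At most 48 − 40 = 8 h to 48 − 28 = 20 h remains after the earliest Day 3 assessment, and 0 h remains if the assessment is at or after 48 h.
- Anaphylaxis: its 4 h limit lies inside the 6 h observation, so it is covered.

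**2. When the next infusion precedes the Day 6 visit**

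An interval of k days puts the next infusion on the prior patient's Day 1 + k.

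| Interval k | Prior patient's day | Before the Day 6 visit? |
|---|---|---|
| 3–4 | Day 4–5 | Always |
| 5–9 | Day 6–10 | Only if the visit is later in its window, or later that day |
| 10 or more | Day 11 or later | Never |

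At the fastest pace, every 3 days, infusions fall on the first patient's Days 4, 7 and 10. One later patient is then infused before a Day 6 visit, and two before the day of a Day 10 visit.

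**3. How often short intervals might occur**

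Releases under this gate number 24 − 3 = 21, because the first patient of each cohort does not follow a same-dose patient. Assume 30 days of final follow-up and two cohort breaks of 20 days.
- 12 months (Protocol 1.22.2, SAP 3.1): (365 − 30 − 40)/21 = 14.0 days on average.
- 18 months (Protocol 1.9.5): (548 − 30 − 40)/21 = 22.8 days on average.

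The average interval is thus longer than the risky range. For illustration, suppose patients arrive at random, so that the interval is 3 days plus an exponential wait with the same overall mean:
- P(3–4 days) = 1 − exp(−2/11.0) = 16.6%; × 21 = 3.5 releases.
- P(3–4 days) = 1 − exp(−2/19.8) = 9.6%; × 21 = 2.0 releases.

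Multiply by the share of patients out of hospital after Day 2, which is not given:

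| Share out of hospital | Affected releases |
|---|---|
| 0% | 0 |
| 50% | 1.0–1.7 |
| 100% | 2.0–3.5 |

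With 30 infused patients there are 27 releases, and the same formula gives 12.7% to 22.3%, or 3.4 to 6.0 at a 100% share.

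**4. Room for a check**

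With daytime dosing, a Day 4 infusion falls 60 h (20:00 to 08:00) to 84 h (08:00 to 20:00) after the prior one. That is 60 − 48 = 12 h to 84 − 48 = 36 h after the stopping window closes.

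**5. The SAP wording**

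With 24 h from awareness to report, an event starting at 24 to 48 h can be reported on time yet after 48 h. Under SAP 3.2 it would then count for suspension only.

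**The case against.** The best reply concerns weight. The study is described as one in hospitalized patients, in-patients are assessed daily, and the affected group may be small or empty. The average spacing of about 14 to 23 days lies beyond the latest Day 6 visit. The 24-hour visit is thorough (examination, vital signs, CBC, coagulation, chemistry, troponin). Escalation needs completed Day 6 visits and review by an investigator, the medical monitor and the DMC (1.9.7). A death, stroke or embolism usually brings medical contact. The arrival model is an assumption, and no rate for an unreported event can be taken from the documents. All of this stands and limits the size of the concern.

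The other safeguards do not close the gap. The sentence in 1.9.2.1 on evaluating all patients for adverse events sets no time. CBCs around a transfusion on Days 1 to 6, and unscheduled visits (1.15.6), happen only if something prompts them. The calls in Tables 6 and 7 follow a withdrawal or a missed visit. The Table 4 monitoring line could be read as daily monitoring to Day 6 for a patient never admitted, but the hospitalization heading and 1.9.2.1 point the other way, and a discharged patient is uncovered on either reading.

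The Appendix B diagram, the DMC charter and some text after 1.22.6.4 were not available to us. The table of contents lists no section between 1.22.6.4 and 1.22.7. A check could still be laid down in the diagram or the charter.

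On the SAP wording, suspension also halts infusions. The mismatch therefore changes the standard for restarting and exposes no extra patient.

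**Conclusion.** The point holds and should be fixed. A site that follows the visible text exactly can release a same-dose infusion without knowing the prior outpatient's state in roughly the second half of the 48-hour stopping window. The schedule gap of 21 to 27 hours follows directly from the visit windows. The number of releases affected is uncertain. It is zero if all patients stay in hospital, and it reaches 2.0 to 3.5 of 21 only if none do and arrivals are random. Wider spacing removes the problem, but the plan does not require it. No probability of harm can be derived from the documents.

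**What to change.** In Protocol 1.9.2.1, Table 4 and SAP 3.1, replace the absence of a report with a documented confirmation by the site, before release, that the prior patient has had no suspension or stopping event. For anyone not in hospital, base it on a phone or chart check for AEs and SAEs made after 48 hours, using the Day 30 method in Table 4, note 3. If the patient cannot be reached, hold the next infusion until status is confirmed by phone or chart. Separately, word the 48-hour and 4-hour criteria in SAP 3.2 by event onset, to match Protocol 1.9.8.

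The routine cost is a short amendment and one CRF line per check. There are at most 21 checks with 24 infused patients, or 30 − 3 = 27 if the approximate enrollment of 30 (Protocol 1.10.1) is infused, since SAP 3.1 counts enrollment from the start of infusion. The last patient of each cohort needs none, because the Day 6 review or the end of dosing follows.

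The real cost is a hold. Table 7 prescribes two calls and then a registered letter, so a hold could last days if the chart gives no answer. SAP 3.1 requires infusion within 4 days of eligibility. A patient found eligible on the prior patient's Day d must be infused by Day d + 4. With the gate at Day 4, that leaves d days of slack (1 to 4 days for d = 1 to 4). A longer hold sends the waiting patient to rescreening.
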